3.3.19 Known history of HIV seropositivity

3.3.20 Need for concurrent treatment with medications that strongly interact with everolimus (CYP3A4 inducers or inhibitors, see **Appendix B**).

3.3.21 History of another malignancy within the last five years except non-melanoma skin cancer, carcinoma in-situ of uterine cervix, uteri, and breast from which the patient has been disease free for at least 3 years. Second primary breast cancers are allowed regardless of the number of years since they were first diagnosed.

3.3.22 Major surgical procedure, open biopsy, or significant traumatic injury within 28 days prior to Day 0, anticipation of need for major surgical procedure during the course of the study. As an example, port placement or core biopsies are not considered major surgical procedures.

3.4 Inclusion of Women and Minorities

Both men and women and members of all races and ethnic groups are eligible for this trial. Minority patients are particularly encouraged to participate.

3.5 Subjects Who Fail to Meet the Eligibility Criteria

[figure not shown]
A subject may fail to meet entrance criteria because of an abnormal laboratory value, vital sign(s), or concurrent medications with strong interactions with the investigational combination. The abnormal screening test(s) may be repeated as soon as the investigator anticipates that it will be within acceptable range to meet eligibility criteria, but must be completed within the 4-week screening phase. Rescreening can be performed only once and the subject is not required to sign a new informed consent form.

If the rescreening test(s) cannot be performed within the 4-week screening phase or return abnormal not meeting the entrance criteria, or the medical condition of the subject deteriorates so that she no

longer meets the eligibility criteria, the subject will be deemed a screen failure and withdrawn from the study.

4. STUDY DESIGN

The principal investigator will hold the IND for the trial (**Appendix F**). This is a single-institution open-label phase I/II study of preoperative treatment with the combination of letrozole, everolimus, and TRC105 in postmenopausal women with newly diagnosed potentially resectable local or locally advanced (T2-T4a-c, N0-2, M0; excluding patients with T4d or inflammatory breast cancer) estrogen and/or progesterone receptor positive, Her2/neu negative breast cancer. Accrual will be halted as a result of any grade ≥ 3 hemorrhage, cerebrovascular and vasovagal adverse events; FDA will be contacted to discuss further accrual or potential need for protocol amendment. Premenopausal women at the time of study enrollment will receive goserelin 3.6 mg subcutaneously q 4 weeks to achieve ovarian suppression. The study consists of 2 parts: a phase I and a phase II part (**figure D**).

4.1 Phase I, dose escalation

The first part of the study will follow the conventional 3+3 dose escalation design. Up to 18 patients will be enrolled. During the first part (phase I, **dose escalation**), the Maximum Tolerated Dose (MTD) of the combination in terms of safety will be determined. The dose of letrozole will be kept the same for all cohorts (2.5 mg PO daily) (**Table 4-1**). The dose of everolimus will be escalated from 5 mg PO daily (cohort 1) to 10 mg PO daily (cohort 2). The dose of everolimus will be de-escalated to 5 mg PO daily (cohort 1) if the dose of 10 mg PO daily is not well tolerated. The dose of TRC105 will be 15 mg/kg q 2 weeks (cohorts 1 and 2). The dose of TRC105 will be de-escalated to 10 mg/kg q 2 weeks (cohort -1) if 15 mg/kg q 2 weeks is not well tolerated. All doses that will be used in this trial have shown to be safe and active in clinical trials. Premenopausal women at the time

of study enrollment will receive goserelin 3.6 mg subcutaneously q 4 weeks to achieve ovarian suppression.

Table 4-1. Cohorts and dose escalations of the phase I part of the study

Cohort	TRC105 (mg/kg IV q 2 weeks)	Everolimus (mg PO daily)
1	15	5
2	15	10
-1	10	5

4.1.1 Definition of a Dose Limiting Toxicity (DLT)

A **dose-limiting toxicity (DLT)** is defined as:

- a) Any grade 3 or 4 non-hematologic toxicity except anorexia, alopecia, nausea (which is not refractory to antiemetics), fatigue, fever without neutropenia;
 - b) Failure to recover to baseline (except alopecia) after delaying the next dose by more than 14 days;
 - c) Grade 3 or 4 neutropenia complicated by fever >38.5°C or infection, or grade 4 neutropenia of ≥7 days duration; or
 - d) Grade 4 thrombocytopenia, or grade 3 thrombocytopenia complicated by hemorrhage.
- In addition, accrual will be halted as a result of any grade ≥3 hemorrhage, cerebrovascular and vasovagal adverse events; FDA will be contacted to discuss further accrual or potential need for protocol amendment.

4.1.2 Dose escalation rule:

Dose escalation will follow the decision rules shown in **table 4-2**.

Table 4-2. Dose escalation rules

Number of Patients with DLT at a Given Dose Level	Escalation Decision Rule
0 out of 3	Enter 3 patients at the next dose level.
1 out of 3	Enter 3 additional patients in the same dose level (for a total of 6 patients at this dose level). If 0 of the 3 additional patients experience DLT, then proceed to the next dose level. If 1 or more of these additional patients experience DLT (i.e., ≥ 2 of 6 total patients), dose escalation will be

	stopped.
≥ 2 out 3	Dose escalation will be stopped.
If MTD not reached	Cohort 2 will be selected for RP2D

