4.1.3 Definition of Maximum Tolerated Dose (MTD)

The **maximum tolerated dose** (MTD) is defined as the highest dose at which 0 out of first 3 or 1 out of total of 6 patients experience DLT during the first cycle of therapy; this dose level will be recommended as RP2D in the second portion of the study. If accrual to cohort 2 (highest dose of both everolimus and TRC105) is completed without reaching the MTD, this dose will be selected as the RP2D. In every cohort, patients withdrawn without receiving study treatment will be replaced, as will patients withdrawn before completing the first cycle of treatment for any reason other than DLT.

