4.3 Study accrual and treatment considerations

It is anticipated that 26 – 38 patients will be enrolled in the study and accrual is expected to be completed in 24 months (see Section **10. STATISTICAL CONSIDERATIONS**). Patients meeting the eligibility criteria and who have signed the consent form will start Letrozole 2.5 mg PO daily, Everolimus 5 or 10 mg PO daily, and TRC105 15 or 10 mg/kg IV every two weeks with the first infusion administered in 2 split doses on days 1 (3 mg/kg) and 4 (12 mg/kg or 7 mg/kg), respectively. Premenopausal women at the time of study enrollment will receive goserelin 3.6 mg subcutaneously q 4 weeks to achieve ovarian suppression. A cycle is defined as 4 weeks of treatment. Breast ultrasound, will be conducted upon completion of each cycle to complement clinical assessments of the size of the tumor(s). The duration of neoadjuvant therapy is 24 weeks or 6 cycles. No extensions of the neoadjuvant therapy beyond 6 months are allowed. After neoadjuvant therapy, patients will undergo surgical treatment and will receive adjuvant therapy (radiation therapy, chemotherapy, hormonal therapy) according to the standard of care or at the discretion of the treating physician. The accrual rate is projected to be approximately 1-2 patients per month. Accrual will be halted as a result of any grade ≥ 3 hemorrhage, cerebrovascular and vasovagal adverse events; FDA will be contacted to discuss further accrual or potential need for protocol amendment.

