Adverse events. The addition of everolimus to letrozole has been associated with a higher rate of dose reductions or interruptions due to adverse events (52.9%) as well as discontinuations (18.8%) compared with letrozole alone (7.6% and 9.1%, respectively) in the neoadjuvant setting⁴. Grade 1 and 2 adverse events were also more frequent in the combination arm (89.8% vs. 63.6% in the letrozole alone arm)⁴. The most frequent adverse events seen in higher frequency in the combination arm as compared to the letrozole alone group include stomatitis (36.5% vs. 6.1%), rash (20.4% vs. 7.6%), asthenia (17.5% vs. 9.8%), fatigue (12.4% vs. 4.5%), anorexia (12.4% vs. 3.8%), headache (10.9% vs. 5.3%), pruritus (13.1% vs. none), dyspnea (7.3% vs. 1.5%), pneumonitis (2.9% vs. none). Laboratory abnormalities seen in higher frequency in the combination arm as compared with the control arm include hypercholesterolemia (16.1% vs. 6.1%), thrombocytopenia (18.2% vs. 0.8%), hyperglycemia (13.1% vs. 3%), increased ALT (11.7% vs. 3.8%), anemia (11.7% vs 0.8%), and neutropenia (9.5% vs. 1.5%).

Grade 3 and 4 adverse events were also more frequent in the combination arm (22.6%) as opposed to the letrozole alone arm (3.8%). Stomatitis (2.2%), fatigue (1.5%), and pneumonitis (2.2%) were the most frequent grade 3 and 4 adverse events seen in more than 1 patients (n=137) associated with the addition of everolimus, while hyperglycemia (5.1%), increased ALT (1.5%), hypokalemia (1.5%), thrombocytopenia (1.5%) constituted the most frequent biochemical grade 3 and 4 adverse events. Serious adverse events associated with everolimus occurred in 7/137 patients: pneumonitis in three patients; pneumonia and mouth ulcers/stomatitis each in two patients; and dyspnea, neutropenia, and thrombocytopenia in one patient each. All three patient cases of pneumonitis resolved within 15 days of everolimus discontinuation. Among the placebo-treated patients, there was one serious adverse event of myocardial ischemia⁴.

Overall, safety data available from completed, controlled and uncontrolled studies indicate that everolimus is generally well tolerated at weekly or daily dose schedules. The safety profile is characterized by manageable adverse events (AEs). These AEs are generally reversible and non-cumulative.

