5.3.3 Dose modifications and delays with TRC105

Modifications. The dose for TRC105 is 10 or 15 mg/kg IV every two weeks and it will be continued until 4 weeks prior to surgery. Dose reductions to 10 mg/kg due to adverse events are allowed and the justification(s) should be documented. Dose reductions below 10 mg/kg are not allowed and if deemed necessary, the patient will be taken off study.

Delays. All infusions of TRC105 should be administered within 3 days of the protocol-specified schedule. The maximum duration that a patient is allowed to withhold TRC105 due to adverse events is 14 days. If TRC105 is delayed > 3 days the first dose of TRC105 following the break needs to be split into two doses; 3 mg/kg should be given on the first day and the remainder of the dose (i.e., 12 mg/kg, or 7 mg/kg in the case of a dose de-escalation) will be given 3 days later and the

methylprednisolone dose should be reinstated. If a patient cannot resume TRC105 after 14 days or it is deemed necessary to withhold the medication again, the patient will be taken off study. Resumption at 10 mg/kg if the subject was receiving 15 mg/kg are allowed with the reinstatement of full premedication, as specified in Section 5.2.3.1.

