Following the appropriate premedication regimen, the patient will receive TRC105 on day 1 and day 15 of every cycle. The first TRC105 dose will be split with 3 mg/kg administered on cycle 1 day 1 and infused over 4 hours (+/- 15 minutes) and 12 mg/kg (or 7 mg/kg if dose is de-escalated) administered on cycle 1 day 4 and infused over 2 hours (+/- 15 minutes), and then the full dose of 15 mg/kg (or 10 mg/kg if dose is de-escalated) given on cycle 1 day 15 and every 2 weeks thereafter and will be administered over a minimum of 90 minutes. The patient must complete at least one 4 hour infusion (+/- 15 minutes) without the development of any infusion reactions, in order to reduce the subsequent TRC105 infusion to 2 hours (+/- 15 minutes) and complete a 2 hour infusion (+/- 15 minutes) without the development of any infusion reactions in order to reduce subsequent TRC105 infusions to a **minimum of 90 minutes**. If the patient develops infusion reactions of any kind they should be managed appropriately (see [Section 5.3.2.1](#)) and the patient is not permitted to reduce the duration of the next planned infusion.

The rate of TRC105 infusion must not exceed 25 mg/min. When the i.v. bag containing TRC105 is empty, flush the i.v. line with a 20 mL normal saline. The dose level, time of transfer to i.v. bag, and the infusion start and stop times must be recorded in the source documents.

If the patient misses a TRC105 dose (i.e., ≥ 18 days between doses), the full premedication (including methylprednisolone) should be reinstated as per the initial infusion and TRC105 dose should be administered over two days as was done for the initial dose.

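### DLT criterion (b) cannot be met inside the first-cycle window for the day 15 or cycle 2 day 1 TRC105 dose, and no minimum cycle 1 exposure is set, so some toxicity in patients who stay on study goes uncounted

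*Combined protocol and SAP*

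**What the plan says.** Section 4.1.1 lists four DLT criteria. Criterion (a) covers grade 3 or 4 non-hematologic toxicity with five exceptions, fatigue among them. Criterion (c) covers neutropenia that is complicated or prolonged at grade 4. Criterion (d) covers thrombocytopenia at grade 4, or at grade 3 with hemorrhage. Criterion (b) is the one tied to retreatment: "Failure to recover to baseline (except alopecia) after delaying the next dose by more than 14 days".

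Section 4.1.3 gives this definition of the MTD: "highest dose at which 0 out of first 3 or 1 out of total of 6 patients experience DLT during the first cycle of therapy". Section 4.3 gives the length of that window: "A cycle is defined as 4 weeks of treatment". Under section 6.1.3, "the patient will receive TRC105 on day 1 and day 15 of every cycle", with the first dose split over days 1 and 4.

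On who counts, section 4.1.3 replaces patients who never received study treatment and "patients withdrawn before completing the first cycle of treatment for any reason other than DLT". Section 7.2.2 makes a patient evaluable for toxicity after one dose of any study drug. Neither section asks for a minimum share of planned cycle 1 doses.

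Section 5.3.3 allows TRC105 to be held for up to 14 days and adds: "Dose reductions to 10 mg/kg due to adverse events are allowed and the justification(s) should be documented". It does not exclude phase I.

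**The concern.** Criterion (b) exists to catch toxicity that prevents the next dose from being given. With a threshold of more than 14 days and a window of 28 days, it is out of reach for doses due in the second half of the cycle. A patient can lose or have reduced the day 15 infusion because of toxicity, remain on study, and be entered in the 3+3 count as having had no DLT at a dose that she did not fully receive.

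The MTD and RP2D are part of the primary endpoint (sections 1.2.1 and 10). The dose chosen is then given to up to 20 phase II patients, for a planned 24 weeks. If toxicity goes uncounted, a dose is more likely to pass than the rule suggests.

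**Working it through.** **Plan's own figure.** The plan gives no operating characteristics for its DLT rule. Its enrolment figures reproduce: 3 cohorts × 6 = 18 for phase I, and 18 + 20 = 38 for the upper study total in section 4.3.

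**Timing.** Inputs: a delay of more than 14 days (4.1.1), a cycle of 28 days (4.3), and TRC105 due on days 1, 4 and 15 and then day 29 (6.1.3 and Table 7-1). The first day on which a delay exceeds 14 days is the due day + 15.
- Day 4 split dose: 4 + 15 = day 19, inside the window.
- Day 15 dose: 15 + 15 = day 30, outside.
- Cycle 2 day 1: 29 + 15 = day 44, outside.
- Latest due day that can qualify by day 28: 28 − 15 = day 13.

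**Exposure.** Planned cycle 1 TRC105 at 15 mg/kg is 3 + 12 + 15 = 30 mg/kg.
- Day 15 dose held until day 29 (a 14-day hold, within section 5.3.3): 15 of 30 mg/kg, or 50%. In cohort -1 it is 10 of 20 mg/kg, also 50%.
- Day 15 dose reduced to 10 mg/kg: 3 + 12 + 10 = 25 of 30 mg/kg, or 83%. Nothing is delayed, so (b) does not apply at all.

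**Where the patient goes under each hold limit.** Section 5.3 allows 7 days for the regimen, section 5.3.2 (headed as phase II) 7 days for everolimus, section 5.3.3 14 days for TRC105, and Tables 5-2 and 5-3 up to 28 days for everolimus.
- Day 15 dose, 14-day limit: the limit runs to day 29, after cycle 1. The patient is neither a DLT nor replaced.
- Day 15 dose, 7-day limit: it runs to day 22. The patient leaves within cycle 1 and is replaced.
- Cycle 2 day 1 dose: the limits run to day 36 (29 + 7) or day 43 (29 + 14), both after cycle 1. The patient is neither a DLT nor replaced under either limit.
- Everolimus: under a 7-day limit no hold reaches 14 days. Under the 28-day limit only a hold that starts by day 13 can meet (b) within the cycle.

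**Toxicities left to (b).** Anemia is not named in (c) or (d), and falls outside (a) if it is read as hematologic. Section 2.1.7 names it as the dose-limiting toxicity of TRC105 in its phase I study, at 15 mg/kg weekly. Sections 5.2.3.3 and 5.2.2 (Table 5-3) tie grade 3 or higher anemia to a TRC105 reduction or hold and an everolimus interruption. Grade 2 stomatitis (interrupted under Table 5-4), grade 3 fatigue, and uncomplicated grade 3 neutropenia or thrombocytopenia are also outside the other three criteria.

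**Illustration of size.** The rates here are assumed, not taken from the documents. A dose passes with 0 of 3, or with 1 of 3 followed by 0 of 3:

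P(pass) = (1 − p)³ + 3p(1 − p)² × (1 − p)³

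- p = 0.15: 0.614 + 0.200 = 0.81
- p = 0.20: 0.512 + 0.197 = 0.71
- p = 0.30: 0.343 + 0.151 = 0.49

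If 15% have a listed DLT and a further 5% or 15% have uncounted toxicity and stay on study, the dose passes with probability 0.81 as written, against 0.71 or 0.49 if those patients were counted. If they are withdrawn and replaced instead, the effective rate is 0.15/(1 − 0.05) = 0.158 or 0.15/(1 − 0.15) = 0.176, and the pass probabilities are 0.80 and 0.76.

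**The case against.** The strongest reply is that few patients fall through. Anyone who meets (a), (c) or (d) is a DLT whether or not doses were lost. Anyone withdrawn before completing cycle 1 for another reason is replaced, so is not counted as tolerating the dose. This stands, and it limits the point to patients who stay on study through cycle 1 with toxicity outside those three criteria. A reader might infer that every patient who loses late cycle 1 doses to toxicity is scored as tolerating the cohort dose; the replacement rule in section 4.1.3 and criterion (a) rule that out. Replacement is not neutral, though: the toxicity leaves the denominator, which is a different bias.

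Second, a day 28 cutoff is inferred. A cycle of 4 weeks of treatment might be read as stretching when a dose is late, or a cycle 1 toxicity confirmed later might be called a first-cycle DLT. That reading is open, but no section states it, and the MTD should not depend on which reading a cohort review adopts.

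Third, the harm is bounded. Escalation has only two levels, phase II allows reductions of both drugs, and adverse event rates in all treated patients are also reported. That is fair, but it does not correct the dose selection itself.

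Fourth, treating every toxicity-caused shortfall as a DLT would be a contestable clinical rule. Agreed; it is not asked for here.

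**Conclusion.** The point holds in limited form. Read as written, criterion (b) cannot count for the day 15 or cycle 2 day 1 TRC105 dose, and no minimum cycle 1 exposure defines a DLT-evaluable patient. A patient who never recovers after a withheld day 15 infusion can be classed as having no DLT with half of the planned TRC105.

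This rests on reading the first cycle as days 1 to 28. For the day 15 dose and for everolimus, whether the patient stays in the count or is replaced depends on which of the conflicting hold limits governs. For cycle 2 day 1 it does not depend on whether 7 or 14 days applies.

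The size is unknown. The pass probabilities are illustrations under assumed rates. A reader might take the 52.9% of patients with reductions or interruptions on letrozole plus everolimus (section 5.2.2) as a measure of the hidden rate. That figure covers 4 months of treatment and says nothing about cycle 1 or the length of a hold, so it does not support any particular value.

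**What to change.** - In sections 4.1.1 and 4.1.3, state that (b) is attributed by onset of the toxicity in cycle 1 and covers any dose due through cycle 2 day 1, even if the 14 days run out after day 28. The cohort decision waits until an open delay resolves.
- Define a DLT-evaluable patient by a minimum of planned cycle 1 exposure at the cohort dose, with the threshold set by the sponsor. Replace patients who fall short for reasons other than toxicity.
- State how toxicity-related omission, reduction or withdrawal in cycle 1 is classified, and whether anemia falls under (a).
- Reconcile sections 4.1.1, 4.1.3, 5.3, 5.3.2 and 5.3.3 with Tables 5-2 and 5-3, so that one set of hold limits applies in phase I.

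No hold limit, dose rule or exposure threshold is proposed here. The cost is amendment wording, some replaced patients, and in some cohorts a wait of about 15 days (day 29 to day 44).

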2.1.7 Clinical studies with TRC105

TRC105 was administered to 50 patients with solid tumors in the context of a phase 1 first-in-human dose escalation study following a 3+3 design³⁵. The maximum tolerated dose was determined at 10 mg/kg weekly; 15 mg/kg every two weeks was equally well tolerated and also resulted in continuous serum concentrations known to saturate CD105 binding sites on proliferating endothelium. Hypoproliferative anemia was the dose-limiting toxicity: above the maximum tolerated dose, at 15 mg/kg weekly, all 3 patients that remained on study through cycle 2 developed dose-limiting grade 3 anemia, and one of the three progressed to grade 4 anemia by cycle 3. Infusion reactions, including some that were serious, were observed following TRC105 administration, usually with the initial dose. Other adverse events most commonly observed with TRC105, either alone or in combination, include fatigue, mucocutaneous telangiectasia resulting in epistaxis and gingival bleeding, flushing, and headache. Classic toxicities associated with VEGF inhibition, including hypertension, proteinuria, and thrombosis, have been seen in isolation. In fact, 3 clinical trials combining TRC105 with bevacizumab are currently ongoing (NCT01564914, NCT01648348, and NCT01332721). Multiple other phase Ib and phase II studies of TRC105 in combination with chemotherapy, with VEGF inhibitors, and as a single agent in patients with advanced prostate, sarcoma, renal cell carcinoma, choriocarcinoma, glioblastoma multiforme, and hepatocellular cancer are currently ongoing^{35,85}.

Collectively, TRC105 allows for the rational therapeutic targeting of malignant angiogenesis while sparing the cardiovascular toxicities of most contemporaneous antiangiogenic agents to which postmenopausal women with preexistent conditions may be particularly predisposed.

Although the completed clinical trials with TRC105 were not designed to assess efficacy, several patients benefitted from the investigational drug. In the phase I study where TRC105 was administered as a single agent in patients with advanced metastatic malignancies and having received a median of 4 prior lines of therapy, 6/44 patients remained progression-free for longer than 4 months³⁵.

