4.4 Rationale for the Study Doses and Design

The safety and efficacy of letrozole and everolimus for 4 months in the preoperative setting have been well established⁴, allowing the use of these agents in combination at their approved therapeutic doses. Nonetheless, the addition of everolimus at 10 mg PO daily was associated with an increase in the adverse events of any grade⁴ suggesting that extension of treatment to 6 months without dose reductions, delays, or interruptions may not be possible. To that end, a dose of everolimus at 5 mg PO daily is selected for cohort 1.

The addition of an antiangiogenic agent with a non-overlapping pharmacokinetic and toxicity profile is anticipated to increase the proportion as well as the magnitude of responses achieved without a significant increment in the rate of adverse events. However, TRC105 has not been administered in combination with letrozole and everolimus before. To that end, the phase I portion of the study is designed to determine the MTD and RP2D. Because of a concern that a dose of 10 mg/kg every two weeks will not allow for continuous serum levels of TRC105 placing patients at risk for infusion reactions each time they receive TRC105, the starting dose for the latter was selected at 15 mg/kg q 2 weeks. Provisions are made for a cohort -1 with a dose of TRC105 of 10 mg/kg in case the dose of 15 mg/kg is not well tolerated.

Preoperative treatment with an aromatase inhibitor has been shown to be superior over tamoxifen⁴⁸. Premenopausal women cannot receive aromatase inhibitors⁵⁰ and in order to benefit from the latter they should become postmenopausal. GnRH analogs can safely achieve ovarian suppression and in fact ovarian suppression in combination with an aromatase inhibitor has been shown already to be superior to tamoxifen in the adjuvant setting⁸⁸.

The primary objective of the study is to establish the safety and tolerability of combining everolimus and TRC105 with letrozole in the preoperative setting for 24 weeks. During the phase II part of the study we will continue to evaluate the safety and tolerability of the investigational combination as well as collect preliminary data about the activity of the regimen.

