5.2.3.3 Management of Anemia

Hypoproliferative anemia was the dose-limiting toxicity in the phase I study³⁵ and may be related to the action of TRC105 on proerythroblasts, the only cells in the bone marrow known to express high levels of CD105. When hemoglobin drops in a patient on the study, it is important to investigate for any ongoing blood loss. A reticulocyte count should be obtained to document the hypoproliferative nature of the anemia associated with TRC105. Anemia should be managed with standard supportive measures including transfusions of packed red blood cells if deemed necessary. If grade 3 or higher treatment related anemia develops, the dose of TRC105 should be reduced from 15 mg/kg to 10 mg/kg or held if the assigned dose is 10 mg/kg until resolution of the anemia.

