8.3.1 Hypoproliferative Anemia

TRC105 was administered to 50 patients as part of a phase 1 first-in-human study of solid tumors. Dose escalation proceeded stepwise, and the majority of adverse events were grade 1 or 2. The MTD was 10 mg/kg weekly, and 15 mg/kg every two weeks was also well tolerated. At 15 mg/kg weekly, all 3 patients that remained on study through cycle 2 developed dose-limiting grade 3 anemia, and one of the three progressed to grade 4 anemia by cycle 3. In all three patients, the anemia resolved following discontinuation of treatment. Anemia has been observed in other trials of TRC105.

The dose-limiting anemia at 15 mg/kg weekly was associated with accumulation of TRC105 and characterized by a low reticulocyte production index. Additional laboratory and clinical evaluations excluded common causes of anemia including blood loss, hemolysis, plasma volume expansion, inadequate erythropoietin, iron deficiency, and vitamin B-12 or folate deficiency. Bone marrow aspiration attempts in the patient with grade 4 anemia yielded insufficient material to permit evaluation of the cause of anemia.

The hypoproliferative anemia was believed to result from TRC105-mediated suppression of proerythroblasts, the only cells in the marrow known to express substantial levels of CD105. Anemia was manageable with standard supportive measures including erythropoietin and packed red blood cell transfusion. One patient dosed in study 105ST101 required dose reduction from 10 mg/kg to 7.5 mg/kg weekly for grade 3 anemia at month 12 and further dose reduced to 6 mg/kg and continued treatment with a minor radiographic response for 20 months. All patients receiving TRC105 should be monitored for anemia and treated appropriately (including possible TRC105 dose reduction).

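### The closed DLT list in section 4.1.1 has no anemia criterion, so cycle-1 anemia that forces the protocol's own TRC105 reduction or hold does not by itself count in the escalation rule

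*Combined protocol and SAP*

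**What the plan says.** Section 4.1.1 lists four alternatives and has no open-ended clause:

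- (a) grade 3 or 4 non-hematologic toxicity, with exceptions;
- (b) failure to recover to baseline "after delaying the next dose by more than 14 days";
- (c) complicated grade 3-4 neutropenia, or grade 4 neutropenia lasting at least 7 days;
- (d) "Grade 4 thrombocytopenia, or grade 3 thrombocytopenia complicated by hemorrhage".

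Section 4.1.3 bases the MTD on DLTs in the first cycle (0 of 3, or 1 of 6). It replaces patients who never start treatment, "as will patients withdrawn before completing the first cycle of treatment for any reason other than DLT". Section 4.3 fixes the window: "A cycle is defined as 4 weeks of treatment".

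On anemia, section 5.2.3.3 calls the hypoproliferative form the dose-limiting toxicity of the TRC105 phase I study and instructs: "If grade 3 or higher treatment related anemia develops, the dose of TRC105 should be reduced from 15 mg/kg to 10 mg/kg". If the assigned dose is already 10 mg/kg, TRC105 is held. Table 5-3 places anemia among the hematologic toxicities and interrupts everolimus for grade 3 or 4. Section 4.4 provides the lower dose level: "Provisions are made for a cohort -1 with a dose of TRC105 of 10 mg/kg".

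Section 5.4.2 and Table 7-1 schedule CBC and chemistry in week 1 (C1D4 in the calendar) and then at the start of each cycle. The C1D15 cell is blank for both, although TRC105 is infused that day and angiogenesis markers are drawn.

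**The concern.** The step from 15 to 10 mg/kg that section 5.2.3.3 imposes on a patient is the same TRC105 step that separates cohort 1 from cohort -1. The protocol treats grade 3 or higher anemia as reason enough to lower the patient's dose, but not as evidence about the dose level. MTD and RP2D belong to the primary endpoint and rest on the cycle-1 DLT count, and the selected dose goes to up to 20 phase II patients. A level at which patients cannot stay on the assigned TRC105 dose because of anemia could therefore be cleared by rule. The replacement clause adds to this, because a patient taken off in cycle 1 for anemia leaves the count altogether.

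A separate, smaller matter is whether the laboratory DLTs that are listed can be observed on the scheduled tests.

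**Working it through.** The plan states no figure for anemia, DLT probability or laboratory timing, so there is none to reproduce.

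**1. Does any item reach anemia?** Item (a) excludes hematologic toxicity, and Table 5-3 classes anemia as hematologic. Items (c) and (d) name other cell lines. None of the four names anemia or hemoglobin. Only (b), which is not specific to a toxicity, remains.

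**2. How far does (b) reach?** It needs a delay of more than 14 days, that is, at least 15.

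- TRC105 at 15 mg/kg: 5.2.3.3 reduces the dose and does not delay it. Section 5.3 leaves withholding to the treating physician, and 5.3.3 allows up to 14 days before the patient goes off study. A withheld day-15 dose passes the mark on day 15 + 15 = 30, after the 28-day cycle.
- TRC105 at 10 mg/kg: 5.2.3.3 holds the dose, and the same day-30 arithmetic applies.
- Everolimus: an interruption completes 15 days by day 28 only if it starts by day 28 - 15 = 13. The only scheduled CBC by then is C1D4. The permitted length is unclear: Table 5-3 tolerates 28 days, the general rule in 5.3 takes a patient off study after 7, and the everolimus-specific 7-day limit in 5.3.2 is headed for the phase II portion.

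**3. Consequence that needs no rate.** Three of three cohort-1 patients have uncomplicated grade 3 anemia in cycle 1 and all drop to 10 mg/kg. Counted DLTs: 0/3. Table 4-2: enter three patients at the next level.

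**4. Illustrative size.** Let o be the per-patient rate of other DLTs and a the cycle-1 rate of grade 3 or higher anemia, both assumed and independent. If anemia counts, p = 1 - (1 - o)(1 - a); as written, p = o. Under Table 4-2, with q = 1 - p,

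P(level cleared) = q³ + 3pq² × q³.

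For o = 0.10 as written: 0.729 + 3(0.10)(0.81)(0.729) = 0.906.

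| Other DLTs (o) | As written | a = 1% | a = 2% | a = 5% | a = 10% |
|---|---|---|---|---|---|
| 5% | 0.973 | 0.963 | 0.952 | 0.910 | 0.824 |
| 10% | 0.906 | 0.891 | 0.875 | 0.824 | 0.730 |
| 20% | 0.709 | 0.691 | 0.674 | 0.622 | 0.536 |

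The documents do not fix a. In 5.2.2, the neoadjuvant letrozole-everolimus trial does not list anemia among its most frequent grade 3-4 laboratory events. In 2.1.3, everolimus-exemestane shows 6% against <1%, grade not stated there. In 8.2.2, pooled phase III everolimus data call grade 3/4 hemoglobin decrease very common, meaning at least 1 in 10. None of these is a cycle-1 rate for this combination.

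**5. Laboratory gap.** Nominal draws fall on days 4 and 29. Assume onset uniform over days 5-28 (24 days); an abnormality lasting L days is seen if a draw falls within it.

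| Duration | Days 4, 29 (now) | Days 4, 15, 29 |
|---|---|---|
| 3 days | 2/24 = 0.08 | 5/24 = 0.21 |
| 7 days | 6/24 = 0.25 | 13/24 = 0.54 |
| 14 days | 13/24 = 0.54 | 24/24 = 1.00 |

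**The case against.** The strongest reply is that the known risk belongs to a different regimen and a later time. In the first-in-human study, at 15 mg/kg weekly, "all 3 patients that remained on study through cycle 2 developed dose-limiting grade 3 anemia", and section 8.3.1 adds: "The dose-limiting anemia at 15 mg/kg weekly was associated with accumulation of TRC105". This trial gives 15 mg/kg every two weeks, which sections 2.1.7 and 8.3.1 describe as well tolerated. Entry requires hemoglobin of at least 10 g/dL. Section 8.3.1 calls the anemia manageable with supportive measures, and not every dose reduction need be a DLT. All of this stands, and it limits the likely consequence. A reader might infer that cohort 1 is already known to cause dose-limiting anemia, or that the RP2D will be set too high. The documents support neither.

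A reader might also infer that anemia can never be a DLT. That goes too far: item (b) is open to any toxicity, TRC105 can be withheld under 5.3 and 5.3.3, and the plan does not say how a delay that starts in cycle 1 and runs past day 28 is attributed. The route is nevertheless indirect and mostly completes after cycle 1.

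Other safeguards exist: real-time monitoring, a monitoring committee, investigator termination for excessive toxicity, adverse event reporting, and the statement in 4.1 that TRC105 is lowered if 15 mg/kg is poorly tolerated. Anemia would thus be managed and reported. None of these changes the count in Table 4-2.

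On laboratory tests, it would be wrong to read the calendar as meaning that no blood count can occur on days 5-28. The week-1 wording, the ±3-day visit window, the 5-working-day assessment window, repeat tests in a deteriorating patient and unscheduled tests all soften the gap. Persisting anemia would show at C2D1. What remains is that transient, asymptomatic laboratory events, and the duration of grade 4 neutropenia, cannot be reliably ascertained from scheduled draws.

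**Conclusion.** The omission is certain on the text. Cycle-1 anemia that makes the protocol reduce or hold TRC105 does not count against the dose level unless it also meets item (b), and a patient withdrawn for it in cycle 1 is replaced. The 3-of-3 case shows that the rule as written can clear a level it should not; it shows logic, not likelihood.

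The effect on the RP2D is not demonstrated. With other DLTs assumed at 10%, counting anemia lowers the chance of clearing a level by 0.015 (0.906 - 0.891) at an assumed 1% cycle-1 rate, and by 0.176 (0.906 - 0.730) at 10%. Both rest on assumed, independent rates.

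This should be fixed because it concerns the primary endpoint and the remedy is short. The laboratory gap is secondary and bears mainly on the neutropenia, thrombocytopenia and chemistry criteria.

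**What to change.** - **Section 4.1.1:** add treatment-related grade 4 anemia, or grade 3 anemia that needs transfusion or triggers the TRC105 reduction or hold in 5.2.3.3, arising in cycle 1 and including the pre-dose C2D1 sample. Naming the hold is needed to cover cohort -1. Because 5.2.3.3 acts on all treatment-related grade 3 or higher anemia, this wording in effect counts all of it.
- **Section 4.1.3:** state that withdrawal in cycle 1 for such anemia counts as a DLT and the patient is not replaced.
- **Section 5.4.2 and Table 7-1, phase I only:** add CBC and chemistry at C1D15. After any grade 4 neutropenia, repeat the CBC, for example every 2 to 3 days until it falls below grade 4 or 7 days have passed, so that the duration criterion can be assessed.

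The cost is a short amendment, one extra routine CBC and chemistry for each of at most 18 patients at an existing infusion and blood-draw visit, and repeat CBCs only after grade 4 neutropenia. The downside is that escalation may stop earlier or move to cohort -1. A cycle-1 criterion will not catch anemia that first appears in cycle 2, which is when it was described in the earlier study.
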